Intervention arms and procedures. All women will be mailed a SHE-Women booklet with the intervention content. Electronic women's health literacy intervention procedures (intervention arm). e will deliver the integrated, multimedia electronic women's health literacy intervention arm of SHE-Women in text-Web format for individuals recently released from jail or have recent involvement with the criminal-legal system (2 years). Two health educators will be responsible for delivering content to participants, with an estimated contact time of ~10 hours pushed to participants over approximately a 5-day period. However, because it is a text-Web intervention, accessing content will be dependent on user engagement with the platform. We will measure uptake of the intervention components as it relates to number of minutes of engagement and length of time (total number of days) that all content was accessed. The lead health educator will describe the study and obtain consent from participants. If participants consent, they will immediately be asked to participate in a baseline survey.

For Aim 1 pilot study participants, this will occur over phone or in person in the community. For Aim 2 RCT participants – all of this will occur at the jail at the participant's time of discharge. Participants will be informed that after consent/ after they leave jail, in order to initiate the program, they should contact the health educator through phone, text message, email, or Facebook message. We estimate that we might lose 30% of women between consent and initiation of the community-based intervention, simply because they do not follow-up with us. Thus, in the Aim 1 pilot study we will over-recruit by 15 women; and in the Aim 2 RCT we will over recruit by 60 women, to make up for potential loss to attrition. To improve rates of follow-up, we will also collect multiple points of expected contact information for the participants: phone numbers, addresses for themselves or family members; usual places of hangout; and Facebook handle. That way, if participants don't reach out to us within three days of consent/release from jail, we can contact them.

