Although the text-Web intervention will be designed to be accessed over a continuous 5-day period; participants will be given a three-week window to access all intervention content, to allow for self-directed completion of the text-Web intervention. As soon as participants access all intervention content, the second health educator will be triggered to complete a post-intervention assessment. The post-assessment will be offered to participants over the phone or through an electronic link to the survey.

We will not provide participants equipment or electronic devices. The goal of this project is to assess whether a text-Web intervention is feasible and effective in real life circumstances, thus, with the participants' own devices. We will not pay for any data usage charges to participants. However, because we are compensating participants for study participation, they can use some of the money from study compensation to cover any data usage costs incurred. There are no limitations on what devices can be used. Though participants will have to either receive initial text messages either through a mobile phone or through a private Facebook message. A third option could be through an email address. Participants will then need to be able to access Web content, but they can do that at any place of their choosing: a mobile phone, a home computer, a public library computer, or at some other place.

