Standard of care discharge planning session (control arm). In the Aim 1 pilot study, participants will only access the intervention arm content. In the Aim 2 RCT, participants will be randomized after consent to the intervention or control arm. The women will be offered a 10-page women's health booklet that utilizes SHE-Women content, but in print form. The booklet will provide simple definitions, screening guidelines, and local health resources for age and risk appropriate cervical, breast cancer, unintended pregnancy, and STI prevention. We will collect multiple points of contact information for the participants: phone numbers, addresses for themselves or family members; usual places of hangout; and Facebook handle, for follow-up. Participants in this arm of the intervention will be contacted 5 days after receiving the standard of care intervention for post-assessment. Similar to the intervention arm, we expect to lose 30% of women to follow-up, thus we will over-recruit by about 30% for the RCT, as described above. Participants will be asked to reach out to us 5 days after or we will contact them for follow-up and to complete the post-assessment over the phone or through an electronic link to the survey.

We wish to note that although we call the control arm the "standard of care," in reality there is no standard discharge planning session in the jails we work with; women are sent out the door with their belongings. But we feel it would be grossly unethical to not provide the control arm with some health information, even if limited.

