Opportunities for human interaction – text messaging and community sessions (both arms invited). To develop a more robust measure of the impact of human interaction on intervention outcomes for Aim 3, we will invite participants from both intervention arms to participate in text messaging with a health educator if they have questions and with the opportunity for attendance at community-based women's health group sessions. To facilitate access to text messaging with a health educator, all participants will be given the health educator's study cell phone number, which she will respond to during business hours. The health educators will also hold quarterly women's health discussion sessions at two public libraries in the Kansas City neighborhoods in which >50% of our participants live.¹⁸ These are public sites where participants know how and when to access services, per our past experiences with them. All participants will be invited, regardless of randomization.

Compensation and retention. Pilot study participants will receive \$25 for completing the intervention, and \$20 for completing the stakeholder interviews. All participants of the RCT will be offered \$50 for completing the intervention. The women in the control arm will receive the same payment to be fair. Participants who complete the COVID-19 interview will receive \$10. Compensation will be placed on a debit card. We have used this method and amount of payment successfully in our previous work with these women.^{3,5,9}

Retention of participants for the annual follow-ups will be accomplished through effective methods that our research teams have developed and used successfully for the last eight years to achieve excellent follow-up

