rates (in our original SHE study, the 3-year follow-up rate is 85%).¹² These methods include supplementing existing participant contact information with names, addresses, phone numbers of participant, family members, friends; places of congregation such as bars, bodegas, street corners, or churches; places for usual drug or mental health treatment (with signed approval to contact facilities), places of previous incarcerations, along with social media hangouts such as Facebook and Snapchat. We will employ previously successful quarterly check-ins during which we verify contact information of participants who will be provided a \$10 incentive. These check-ins will last 5 minutes at most. The only topic to be discussed at the check-in is the verification of contact information (have phone numbers changed? Addresses? Or any other contact information change that we should know about?). Check-ins will primarily be conducted over the phone, but could also occur over text message, private Facebook message, email, or by us writing a participant a letter and the participant calling or writing us back. In rare cases we could also conduct check-ins in person, if the participant would prefer to see us in the community.

Participants will receive \$50 for each follow-up interview, which both compensates their time and allows us to retain participants over time. In our past studies this dollar amount hits the right balance of providing an incentive of value, but not so high as to coerce participants into meeting with us. It is a reality that only one-third of the women are employed, while the rest scrape money together from benefits, under the table work, or trade of sex.^{42,43} Thus, our compensation, while minimal, is a meaningful source of additional income.

Participants will not receive compensation for participation in key stakeholder interviews, since we are only inviting a subsample to participate. We do not want selected participants to be unfairly compensated, when others who were not invited did not receive compensation. In order to not waste participants' time, we will tack on these key stakeholder interviews to regularly scheduled follow-up interviews. Participants will also not receive compensation for communicating with the health educator via text messages or attendance at group sessions, since those are designed to be community-based activities for which participants elect to attend.

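### The RCT pays for completing Web content that it also measures as uptake, and does not say that intervention women who do not finish are paid or assessed post-intervention

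*Combined protocol and SAP*

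**What the plan says.** Compensation and retention sets the RCT payment at $50 "for completing the intervention. The women in the control arm will receive the same payment to be fair". Pilot women receive $25 on the same completion condition. Each follow-up interview earns a further $50; the surrounding text concerns the annual follow-ups, and it is not said whether the immediate post-intervention assessment counts as one. The next paragraphs add: "Participants will also not receive compensation for communicating with the health educator via text messages or attendance at group sessions".

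Intervention arms and procedures describes the electronic arm "with an estimated contact time of ~10 hours pushed to participants over approximately a 5-day period", and "participants will be given a three-week window to access all intervention content". Access to all content triggers the post-intervention assessment. The same section also has the Day 5 message invite women to complete it. For controls, the control-arm section says: "The women will be offered a 10-page women's health booklet that utilizes SHE-Women content, but in print form". They are contacted for the assessment 5 days after receiving their material. That section expects a 30% loss, similar to the intervention arm.

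Outcomes and instruments lists uptake of the Web components as a feasibility and perception outcome for Aims 1 and 3. Data analysis uses uptake as a predictor of literacy and screening outcomes in the Aim 3 mixed models, and handles missing data by MCMC multiple imputation with auxiliary variables.

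**The concern.** There are two separate problems.

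First, money attached to finishing the content acts directly on the uptake measures: minutes, days, clicks and response times. Planned reports on feasibility and on Web uptake (Table 3, Manuscripts #1 and #7) would describe use under that payment. A reader planning a rollout without payment could take them as ordinary use. The Aim 3 models inherit the same condition, because part of the variation in uptake may reflect response to the payment.

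Second, the immediate literacy outcome may be observed mainly in intervention women who finished, but in controls regardless of what they read. If finishers gain more than non-finishers, the observed intervention mean is too high and the comparison favours the intervention. The estimate then drifts from the effect of being assigned SHE-Women toward the effect of finishing it. The payment wording reinforces this, because a woman who stops part-way has no stated payment to stay for the assessment.

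**Working it through.** **Side by side, from the sections above**

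| | Intervention arm | Control arm |
|---|---|---|
| Amount | $50 | $50 |
| Stated condition | completing the intervention | none stated |
| Material | about 10 hours of Web content | 10-page booklet |
| Route to first post-intervention assessment | all content accessed, up to three weeks; also a Day 5 invitation | contact 5 days after the booklet |
| Non-finishers paid? assessed? | not stated | no completion requirement stated |

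The difference in amount is $50 - $50 = $0. Only the stated condition and the effort differ: $50 / 10 hours = $5 per hour for a woman who does all the content. No rate can be formed for controls, because no task is stated.

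**What imputation can do.** If the all-content trigger is followed literally, no non-finisher supplies an immediate post-intervention value. The imputation model then has no observed non-finisher at that visit, and must borrow from finishers and from the woman's own baseline and 1-year data. That is adequate only if these recorded variables explain the difference between finishers and non-finishers. The Power section's statement that missing data will be fully recovered cannot be assumed here.

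**Can the bias be sized?** Table 4 gives 220 at initiation and 200 post-intervention: 220 - 200 = 20 lost, 20/220 = 9.1%. It is not split by arm, and no figure is given for non-finishing, for unpaid uptake, or for how non-finishers score. What follows is therefore an illustration on assumptions, before any imputation.

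*Yardstick.* The Power section defines f as the group difference in change and takes f = 0.12. For two groups and two time points, each interaction cell effect is one quarter of the difference in change, so f = difference/(4 SD) and the difference is 4 x 0.12 = 0.48 SD.

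*Route A: bias = share of intervention women missing x gap.* Assume 110 per arm at initiation, non-finishers gain 0.2 to 0.5 SD less than finishers, and control losses unrelated to outcome.
- Losses split evenly: 10/110 = 9.1%. Bias 0.091 x 0.2 = 0.018 to 0.091 x 0.5 = 0.045 SD, or 4% to 9% of 0.48.
- All 20 in the intervention arm: 20/110 = 18.2%. Bias 0.036 to 0.091 SD, or 8% to 19% of 0.48.
- If losses are equally frequent and equally related to outcome in both arms, the bias is nil.

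*Route B: bias in each arm = rho x phi(z)/p*, where p is the proportion assessed, z the matching normal quantile, phi the normal density, and rho the correlation between being assessed and the outcome. Assume 130 per arm, about 200 assessed in all, rho 0.1 to 0.3.
- 70% against 84% assessed: difference 0.02 to 0.06 SD.
- 60% against 94% assessed: difference 0.05 to 0.16 SD.

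Power is not the issue. In the last case about 78 and 122 women are assessed, and the effective N is 4 x 78 x 122/200 = about 190 against 200 when balanced.

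**The case against.** The strongest reply is that this is an undefined trigger, not a shown bias. The same sum is offered to all RCT participants. The protocol also applies the word intervention to the control condition, so completion could mean completing the study phase in either arm. The arms are expected to lose similar proportions, re-incarceration is listed as one cause of non-completion, and an intent-to-treat analysis with multiple imputation is planned. Any selection also comes mainly from the assessment trigger rather than the money. Much of this stands: it rules out a definite bias figure, and it means that changing the payment alone would leave the trigger in place.

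Four stronger readings are tempting, and the documents do not support them.
- A reader might infer that women are paid differently by arm for reaching the assessment. No text ties the $50 to that assessment in either arm.
- A reader might infer that controls have nothing to complete. That rests on silence; they have a booklet and a scheduled assessment.
- A reader might see paid completion as contradicting "The goal of this project is to assess whether a text-Web intervention is feasible and effective in real life circumstances". The sentence goes on to explain this as use of women's own devices, and the same paragraph discloses compensation.
- A reader might expect Aim 3 to set paid Web uptake against unpaid texting and sessions. No comparison of those rates is planned; uptake is summarised descriptively and related to outcomes.

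The reply does not remove two facts. The payment is worded as a reward for completion while uptake is measured, and nothing provides for assessing a woman who does not finish.

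**Conclusion.** The point holds in two parts. The uptake results will describe use under a completion payment and must be read that way; how far the payment raises uptake cannot be computed, because no unpaid rate is given. The immediate post-intervention literacy comparison is open to selection toward finishers in the intervention arm.

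The size of that selection is not determined by the documents. The illustrations run from nil to 0.16 SD before imputation and rest on assumed loss patterns, score gaps and correlations; they are not estimates. The direction, in favour of the intervention, assumes that finishers gain more. The second part concerns the immediate assessment only: the annual follow-ups are paid per interview, with no content condition stated.

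**What to change.** 1. In Compensation and retention, replace the completion payment with the same $50 in both arms for completing the post-intervention assessment, regardless of how much content was accessed. Treat the pilot's $25 likewise.
2. In Intervention arms and procedures, offer that assessment to every intervention woman no later than the end of the three-week window, whether or not all content was accessed, and reconcile this with the Day 5 invitation. Without this step the all-content trigger would remain and the payment change would not reach non-finishers.
3. For women already enrolled under the present wording, report Web uptake as uptake under a completion payment.

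The cost is a short amendment to protocol and consent. The amount offered per woman is unchanged, although some women who would not have finished the content will now be paid for the survey. Content completion may fall somewhat. The protocol calls the RCT ongoing and does not say how many enrolments remain, so steps 1 and 2 may reach only part of the sample; step 3 applies in any case.

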Power. The sample size for the Aim 1 feasibility study is based on our original SHE study pilot and expanded to allow for rigorous testing and refining of modality.²⁶ The sample size of N~200 for the Aim 2 RCT was determined to provide satisfactory power ($\geq 80\%$) for this study in addressing the specific aims, which depends on the following parameters: number of participants (n), number of measurements (t=3 for health literacy for screening; t=4 for screening/risk reduction practices), effect size (f) as group difference in change, correlation between repeated measures (r), and attrition rate. The effect sizes estimated from the original SHE study were in the small to moderate range—for health literacy (8 domains), average $f=0.13$ at immediately post-intervention and 0.16 at 1-year post-intervention; $f=0.17$ for cervix screening and 0.12 for condom use during the last intercourse at 1-year post-intervention. Although effect sizes for breast cancer screening and STI screening are not available from the original SHE study, we expect similar, small to moderate effect sizes for these outcomes. Thus, we conservatively assumed the smallest observed effect size of $f=0.12$ for our power calculation. The correlations between repeated measures observed in the original SHE study were $r=0.46$ on average, with the range of 0.39-0.75 between baseline and immediately post-intervention and 0.25-0.61 between baseline and 1-year post-intervention. Power analysis of these data ($f=0.13$, $t=3$ or 4, $r=0.46$) and G*Power 3.1.9.2 indicated that a sample of 124 women will produce $\geq 80\%$ power for both health literacy (80%) and screening/risk reduction behaviors (85%). In our original SHE study, the 3-year follow-up rate was 85%. Conservatively assuming a high attrition rate up to 40%, we will recruit ~200 women at baseline to adequately power the SHE-Women study—i.e., maintain $\geq 80\%$ power even with a low follow-up rate as small as 60%. As

Table 4. Expected attrition over study period

	Aim 1 feasibility Target N~20	Aim 2 RCT Target N~200	Aim 3 (same as Aim 2)
Consent and baseline	20	260	--
Intervention initiation	15	220	--
Post-intervention	10	200	--
1 year follow-up	--	170	--
2-year follow-up	--	160	--
3-year follow-up	--	150	--

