Using quantitative data from the pilot trial of the SHE-Women text-Web intervention, we will conduct descriptive analysis and bivariate tests to explore women's health literacy (knowledge, beliefs, and self-efficacy) for screening related to cervical, breast cancer, birth control, and STIs (Aim 1). The results including effect sizes estimated for the outcome will be utilized for refinement of the intervention content and modality. To test the hypothesis that SHE-Women will be more effective than standard of care at improving outcomes (Aim 2), we will utilize mixed modeling techniques for repeated measures, separately for each outcome variable: health literacy for screening and screening/risk reduction practices. General/generalized models will evaluate the effects of the intervention by estimating overall group difference across measurements (i.e., group effect), change over time (i.e., time effect), and group difference in change (i.e., group-by-time interaction). In other words, we will evaluate whether the intervention vs. control group improves in outcomes over time. The models will account for the impacts of sociodemographic characteristics as well as other cross-cutting risk factors including tobacco use, alcohol use, criminal justice involvement, intimate partner violence, lack of continuous health care coverage or primary care contact, etc. (covariates), thereby providing unbiased estimates of the intervention effects. The models for screening/risk reduction behaviors will also consider knowledge about cervix cancer, breast cancer, birth control, or STI as an additional covariate for the respective outcome variable. Incorporating participant tracking data, descriptive analysis and bivariate tests will demonstrate the pattern and uptake of various intervention components as measured by number of participants who responded to text messages; clicks on the Website; interactive clicks on the Website, e.g. through real-time assessment of knowledge; time elapsed between text messages and Website clicks; number of outreach messages (through text, phone, or Facebook); Facebook posts/messages; chats with health educator; total minutes of contact through text, Web, chat, Facebook with each participant; and attendance at community sessions (Aim 3). General/generalized mixed modeling for repeated measures will assess the impacts of the uptake on each outcome variable of health literacy for screening and screening/risk reduction practices while controlling for the impact of sociodemographic characteristics and other risk factors. A proper covariance structure for repeated measures will be chosen for each outcome variable based on model fit (i.e., likelihood, Akaike Information Criterion, adjusted Bayesian Information Criterion). Statistical significance will be determined at 0.05 alpha level, and all analyses conducted using SAS 9.4⁵⁹

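### The Power paragraph enters a single-visit effect size unchanged into three- and four-measurement tests and gives two values for it (0.12 and 0.13), so at least 80% power at 60% follow-up is not supported for the smallest observed effect.

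*Combined protocol and SAP*

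**What the plan says.** All of the inputs stand in the Power paragraph of the Approach section.

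- It defines the "effect size (f) as group difference in change" and gives no formula for it.
- The parent-study values are each tied to a visit, first for literacy (averaged over eight domains) and then for two behaviours: "average $f=0.13$ at immediately post-intervention and 0.16 at 1-year post-intervention; $f=0.17$ for cervix screening and 0.12 for condom use". Both behaviour values are for 1 year.
- It lists the "number of measurements (t=3 for health literacy for screening; t=4 for screening/risk reduction practices".
- It says that the smallest observed value, 0.12, was assumed as the conservative choice. The line that reports the G*Power run prints f=0.13, with r=0.46.
- The run "indicated that a sample of 124 women will produce" 80% power for literacy and 85% for screening and risk reduction. Recruiting about 200 is then said to keep power at 80% or more even if only 60% are followed up.

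The Data analysis section confirms that the models test the "group difference in change (i.e., group-by-time interaction" and adds: "Statistical significance will be determined at 0.05 alpha level". Table 4 expects 170 women at 1 year and 150 at 3 years.

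**The concern.** Cohen's f for an interaction depends on how many measurements it is averaged over. A value from baseline and one follow-up visit is not the value for the same effect spread over three or four measurements. If f is held fixed while measurements are added, the noncentrality grows in proportion to their number. Power then rises because a larger effect has been assumed without saying so.

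The paragraph describes no conversion and no pattern of effect over the visits. It also disagrees with itself on which f was used. At stake are the two stated powers, the figure of 124 on which the recruitment target rests, and the assurance about 60% follow-up.

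**Working it through.** **Inputs.** N=124, r=0.46, t=3 or 4, f=0.12 or 0.13 (Power paragraph); alpha 0.05 (Data analysis); two equal arms (Table 3, about 100 each).

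**Step 1: reproduce the plan's figures.** For the within–between interaction with two groups, as in G*Power, λ = f²·N·t/(1−r), with df1 = t−1 and df2 = (N−2)(t−1). Power comes from the noncentral F.

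| f | t | λ | Power, N=124 |
|---|---|---|---|
| 0.12 | 3 | 0.0144×124×3/0.54 = 9.92 | 80.7% |
| 0.12 | 4 | 0.0144×124×4/0.54 = 13.23 | 87.3% |
| 0.13 | 3 | 0.0169×124×3/0.54 = 11.64 | 86.9% |
| 0.13 | 4 | 0.0169×124×4/0.54 = 15.52 | 92.4% |

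A multivariate version with f=0.12 gives 80.2% and 86.5%. So unscaled 0.12 best explains 80% and 85%. The printed 0.13 comes near only with a nonsphericity correction of 0.75 that the plan does not mention (78.9% and 85.7%), and the first of these is below the stated 80%.

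At 120 women, which is 60% of 200, unscaled f=0.12 gives 79.3% (t=3) and 86.1% (t=4).

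**Step 2: convert the single-visit effect.** Assumption: each parent f is a two-group interaction between baseline and one visit. Then f = δ/4, where δ is the difference between arms in change, in SD units. So f=0.12 means δ = 4×0.12 = 0.48. If δ is the same at every follow-up visit, f = δ·√(t−1)/(2t):

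- t=2: 0.48×1/4 = 0.120
- t=3: 0.48×1.414/6 = 0.113
- t=4: 0.48×1.732/8 = 0.104

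Conversely, holding f=0.12 at t=4 requires δ = 0.12×8/1.732 = 0.554. That is 15% above 0.48.

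**Step 3: power with the converted f, omnibus test.**

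| Single-visit f | Analysed N | t=3 | t=4 |
|---|---|---|---|
| 0.12 | 120 | 74.1% | 73.7% |
| 0.12 | 124 | 75.6% | 75.2% |
| 0.12 | 138 | 80.3% | 80.1% |
| 0.12 | 150 | 83.7% | 83.7% |
| 0.12 | 170 | 88.3% | 88.4% |
| 0.13 | 124 | 82.4% | 82.4% |

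Simulation (20,000 runs per case) gives 75.8% and 75.4% for f=0.12 at N=124.

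**Step 4: the other reported effects, same reading, N=124.** The literacy averages (0.13, then 0.16) give 91.1% at t=3. Cervix screening (0.17) gives 97.3% at t=4.

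**Step 5: sensitivity, single-visit f=0.12, N=124.**

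- Effect rising linearly to δ at the last visit: 62.3% (t=3), 60.8% (t=4).
- Sustained effect tested by a one-df contrast (mean of follow-ups minus baseline): 83.8% and 87.8%.
- r=0.25: 60% and 59%. r=0.61: 88.5% and 88.6%.
- If f is instead half the standardised difference at one visit, δ = 2×0.12 = 0.24, and power is about 24% and 23%.
- If f already describes the whole profile, no conversion is needed: 80.7% and 87.3%.

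**The case against.** The strongest reply is that the documents never say how f was obtained. The relation f = δ/4 and the flat profile are assumptions. The progress report adds doubt: it describes a waitlist comparison for the post-intervention results, but an observational follow-up design and 1-year screening set against baseline. A two-arm contrast at 1 year, the source of 0.12, cannot be taken for granted. This stands, and it makes the 75% conditional. It does not rescue the stated figures. They need an f that already describes the full profile, which fits poorly with values labelled by visit and with a 1-year value used for a test running to year 3.

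Two further points stand. The test matters: a one-df contrast keeps power above 80% for a sustained effect, and there power does rise with more visits. Condom use at last sex also appears to be a binary outcome. The plan allows generalized models with covariates, so a Gaussian repeated-measures figure only approximates the power of the planned analysis.

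A reader might infer that 124 women give 75% power, not 80% or 85%, for both outcome families, or that the trial is too small. The documents do not support either. Among the effects reported, only condom use falls below 80% on this reading; f=0.13 stays at 82%; and the numbers expected in Table 4 give about 84% to 88% even for f=0.12.

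**Conclusion.** The point holds in a limited form. The paragraph contradicts itself on f, and it carries a single-visit value into longer tests without stating a conversion or a profile. Unscaled 0.12 is the input that best explains 80% and 85%.

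If 0.12 is a two-group, baseline-to-one-visit effect that is sustained, and the omnibus interaction is tested with r=0.46, the shortfall at 124 women is about 4 points against the stated 80% and about 10 against the stated 85%. At 60% follow-up, power is about 74%, so the assurance of 80% is not supported for the smallest observed effect. That affects the plan's worst case. It does not show that the recruitment target is inadequate.

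**What to change.** In the Power paragraph:

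1. Reconcile 0.12 with 0.13 and say which was used.
2. State how each parent-study f was computed: which groups, which measurements, which standardiser.
3. State the assumed pattern of effect over the visits and the test that is powered (omnibus interaction or a named contrast).
4. Convert the visit-specific effect to that pattern, and restate power at 120–124 and at the 150 women of Table 4. On the sustained, omnibus reading with f=0.12 these are about 74–76% and about 84%, and about 138 analysed women are needed for 80%. These figures should go in only if step 2 confirms the reading.
5. Remove the gain from 80% to 85% unless the stated pattern and test support it, and reword the 60% follow-up assurance to match.

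The cost is one rewritten paragraph, one rerun of the calculation, and a slightly less favourable stated power. No extra enrolment is asked for.
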